8.5 Outcome

The outcome of an AE will be recorded on the AE eCRF as follows:

- Recovered / Resolved
- Recovering / Resolving
- Recovered / Resolved with Sequelae
- Not Recovered / Not Resolving
- Fatal
- Unknown

8.6 Pregnancy

A pregnancy is not an AE. If a female participant or the female partner of a male study participant becomes pregnant while enrolled in the study following administration of study drug and within 30 or 90 days, respectively, after administration of the last dose of study drug, the Sponsor must be notified within 24 hours of the Investigator learning of the

pregnancy. Administration of study drug will be discontinued immediately, and the participant or the female partner of a male study participant will be followed through the outcome of the pregnancy. The Investigator is required to provide all the relevant information to the Sponsor using the Pregnancy Information Form to do so.

The pregnancy will be followed through delivery. If the pregnancy results in a congenital anomaly/birth defects, this will be considered and reported as an SAE as per definition detailed in [Section 8.8](#).

8.7 Clinical Laboratory Adverse Events

Abnormal laboratory findings (eg, clinical chemistry, hematology and urinalysis) or other abnormal assessments (eg, ECG, vital signs) *per se* are not reported as AEs. However, those abnormal findings that are deemed clinically significant or are associated with signs and/or symptoms must be recorded as AEs if they meet the definition of an AE, as described in [Section 8.2](#) (or recorded as an SAE if they meet the criteria of being serious, as described in [Section 8.8](#)). Clinically significant abnormal laboratory or other abnormal findings that are detected after consent or that are present at baseline and worsen after consent are included as AEs (and SAEs if serious).

The Investigator should exercise his/her medical and scientific judgment in deciding whether an abnormal laboratory finding or other abnormal assessment is clinically significant. Usually, the abnormality should be associated with a clinically evident sign or symptom, or be likely to result in an evident sign or symptom in the near term, to be considered clinically significant. A clinically significant laboratory abnormality in the absence of clinical symptoms may jeopardize the participant and may require intervention to prevent immediate consequences. For example, a markedly low serum glucose concentration may not be accompanied by coma or convulsions, yet be of a magnitude to require glucose administration to prevent such sequelae.

8.8 Serious Adverse Events

8.8.1 Definition of Serious Adverse Events

A SAE is any untoward medical occurrence that at any dose:

- Is life-threatening
 - An AE is considered life-threatening if, in the opinion of either the Investigator or the Sponsor, its occurrence places the participant at immediate risk of death. It does not include an AE that, had it occurred in a more severe form, might have caused death.
- Results in death
- Requires inpatient hospitalization (ie, admission) or prolongation of existing hospitalization. Except:
 - An emergency room visit without hospitalization is not considered fulfilling the serious criteria of hospitalization.

- Planned hospitalization or surgical procedures for an illness or disease which existed before the participant was enrolled in the clinical trial is not considered an SAE unless the condition deteriorated in an unexpected manner.
- Results in persistent or significant disability/incapacity
- Is a congenital anomaly/birth defect
- Is an important medical event
 - An event that does not fulfill any of the serious criteria above, but is considered to be clinically significant and may jeopardize the participant, or when medical or surgical intervention may be required to prevent one of the outcomes listed above.
 - Examples of such events include, but are not limited to: laboratory abnormalities meeting the criteria for suspected drug induced liver injury (DILI) or QT prolongation that lead to permanent study drug discontinuation, allergic bronchospasm requiring intensive treatment at an emergency room or at home, blood dyscrasias, convulsions that do not result in inpatient hospitalization, or the development of drug dependency or drug abuse.

8.8.2 Recording Adverse Events and Serious Adverse Events

All AEs and SAEs spontaneously reported by the participant and/or in response to an open question from study personnel or revealed by observation, physical examination or other diagnostic procedures will be recorded on the appropriate page of the eCRF. Any clinically relevant deterioration in laboratory assessments or other clinical finding is considered an AE and must be recorded on the appropriate pages of the eCRF. When possible, signs and symptoms indicating a common underlying pathology should be noted as one comprehensive event.

8.8.3 Reporting Serious Adverse Events

In order to meet the requirements for expedited reporting of SAEs meeting specific requirements to applicable regulatory authorities and Institutional Review Boards (IRBs)/ Independent Ethics Committee (IECs)/ Research Ethics Boards (REBs), all SAEs must be reported to the Sponsor per the Study Manual within 24 hours from the time site personnel first become aware of the event by completing the SAE form and emailing it to the below:

[contact]

Initial notification of an SAE by telephone must be confirmed in writing within 24 hours by completing the SAE form. As further information regarding the SAE becomes available, such follow up information should be documented and sent to ***[contact]***.

All SAEs must be followed by the Investigator to resolution or medical stabilization.

Withdrawal from the study in the event of a SAE and therapeutic measures taken shall be at the discretion of the Investigator. A full explanation for the discontinuation from the study should be made in the eCRF.

8.8.4 *Reporting SAEs to Regulatory Authorities and IRB/IEC/REB*

The reporting of any SAEs to applicable regulatory authorities will be the responsibility of the Sponsor in compliance with applicable country regulations. All SAEs must be reported to the IRB/IEC/REB by the Investigator in accordance with their regulations.

9 MONITORING AND MANAGEMENT OF ELEVATED LIVER BIOCHEMISTRY TESTS

Reference ranges for key liver biochemistry tests are shown in [Table 2](#).

Table 2 Reference Ranges for Key Laboratory Liver Function Tests

Parameter	Reference Range
Alanine aminotransferase (ALT)	10 – 55 U/L
Aspartate aminotransferase (AST)	10 – 40 U/L
Alkaline phosphatase (ALP)	45 – 115 U/L
Total bilirubin	0.0 – 1.0 mg/dL

Participants who experience treatment-emergent elevations in serum ALT or AST that reach the thresholds listed below must be managed carefully:

- **ALT or AST $\geq 8 \times$ ULN**
- **ALT or AST $\geq 5 \times$ ULN for more than 2 weeks**
- **ALT or AST $\geq 3 \times$ ULN and (Total Bilirubin $>2 \times$ ULN or international normalized ratio [INR] >1.5)**
- **ALT or AST $\geq 3 \times$ ULN with liver-related symptoms including the appearance of fatigue, nausea, vomiting, right upper quadrant pain or tenderness, fever, rash, and/or eosinophilia ($> 5\%$)**

Participants must return to the study site for reevaluation within 48 to 72 hours after the abnormal laboratory results become available for confirmatory testing serum levels of ALT, AST, total and direct bilirubin, and INR. A PK sample must be obtained at the same time that the repeat clinical laboratory samples are drawn, and the date and time of the PK draw and the last dose of study drug (and that of pirfenidone or nintedanib, if applicable) must be recorded in the eCRF.

If prompt evaluation is not possible within 48 to 72 hours after receipt of the abnormal laboratory results, study drug should be interrupted immediately (date of last study drug dose [and that of pirfenidone or nintedanib, if applicable] must be recorded in the eCRF), and the participant must return to the study site as soon as possible for reevaluation. The Sponsor Study Director should be notified of laboratory abnormalities and any clinical symptoms within 48 hours of the availability of laboratory results and/or assessment of clinical symptoms.

Participants who experience treatment-emergent elevations in **ALT or AST $\geq 2 \times$ ULN** (but $< 3 \times$ ULN) should be managed as follows:

- Participants must return to the study site for reevaluation within 48 to 72 hours after the abnormal laboratory results become available for confirmatory testing serum levels of ALT, AST, total and direct bilirubin.
- A PK sample must be obtained at the same time that the repeat clinical laboratory samples are drawn, and the date and time of the PK draw and the last dose of study drug (and that of pirfenidone or nintedanib, if applicable) must be recorded in the eCRF.

In the absence of liver-related symptoms and/or elevations in total bilirubin or INR, participants with confirmed treatment-emergent elevations in ALT or AST $\geq 2 \times$ ULN (but $< 3 \times$ ULN), may continue dosing of study drug and be monitored closely with frequent (eg, at least once weekly) hepatic laboratory testing and clinical assessments using unscheduled visits, including a thorough causality evaluation and in consultation with the Sponsor Study Director.

Study drug must be permanently discontinued in the event of confirmed elevations in serum ALT or AST that meet the following criteria for suspected acute DILI, based on the Guidance for Industry on Drug-Induced Liver Injury: Premarketing Clinical Evaluation (FDA, 2009).

Criteria for permanent discontinuation of study drug for confirmed ALT or AST elevations:

- Confirmed ALT or AST $\geq 3 \times$ ULN with (Total Bilirubin $> 2 \times$ ULN or INR > 1.5) and/or, presence of liver-related symptoms, if no other etiology is suspected/confirmed and liver enzymes are sustained following interruption of study drug
- Confirmed ALT or AST $\geq 5 \times$ ULN for more than 2 weeks, if no other etiology is suspected/confirmed and liver enzymes are sustained following interruption of study drug
- Confirmed ALT or AST $\geq 8 \times$ ULN, if no other etiology is suspected/confirmed and liver enzymes are sustained following interruption of study drug

All elevations in serum ALT and/or AST that are confirmed upon repeat testing AND that meet the criteria for suspected DILI (as listed above) must be reported to the Sponsor Study Director within 48 hours. The participant must permanently discontinue study drug immediately and continue to be followed for close monitoring and causality and clinical evaluation as follows:

- Repeat liver enzyme and serum bilirubin tests at least once a week until abnormalities stabilize (i.e., levels are clinically comparable to baseline values or baseline grade of abnormality) and the participant is asymptomatic
- Obtain a detailed history of symptoms and prior or concomitant diseases

- Obtain a history of concomitant drug use (including nonprescription or over-the-counter medications and herbal and dietary supplement preparations), alcohol use, recreational drug use, and special diets
- Rule out acute viral hepatitis types A, B, C, D, and E; alcoholic hepatitis; hypoxic/ischemic hepatopathy; and biliary tract disease
- Obtain immunoglobulin G1 (IgG-1), antinuclear antibody (ANA), anti-smooth muscle antibody (anti-SMA), anti-liver-kidney microsome type 1 (anti-LKM1), and anti-liver cytosolic antigen type 1 (anti-LC1) levels to be compared with baseline values, to rule out autoimmune hepatitis
- Obtain a history of exposure to environmental chemical agents
- Consider a gastroenterology or hepatology consultation, which may include a liver biopsy, for definite diagnosis

For participants with confirmed elevations in liver enzymes (as described above) warranting temporary interruption of study drug but not meeting permanent drug discontinuation criteria as stated above, more frequent hepatic laboratory testing and clinical assessments must be conducted using unscheduled visits, including a thorough causality evaluation and in consultation with the Sponsor Study Director.

Reinitiation of study drug can only be considered if another etiology is identified and confirmed and if liver abnormalities have returned to baseline values. **The decision to restart study drug must be discussed and approved in consultation with the Sponsor Study Director prior to reinitiation.**

Participants who permanently discontinue study drug due to potential liver toxicity must be followed for close monitoring until abnormalities stabilize to baseline levels or baseline grade of abnormality and the participant is asymptomatic. Participants should be encouraged to remain in the study and completed all scheduled visits and assessments. Long-term follow-up information should be provided for participants who permanently discontinue drug due to potential liver toxicity, including information on immunosuppressive therapy and new liver histology.

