6.2 Dose Modifications and Interruptions

There will be no dose modifications of the study drug. If the study drug needs to be interrupted for safety or tolerability issues, this should happen, as feasible, in consultation with the Sponsor Study Director, who together with the Investigator will assess and decide whether the study drug interruption should be temporary or permanent on a case by case basis. Participants who discontinue study drug for safety reasons prior to completion of 12 weeks of treatment will be asked to remain in the study to complete all remaining assessments; if this is not feasible, then they will be asked to return to the clinic for an early termination visit.

Dose modifications or interruptions of pirfenidone or nintedanib treatment may be implemented only for safety and tolerability reasons (e.g., liver enzyme elevation; see [Section 9](#)), in accordance with their corresponding prescribing information and in consultation with the Sponsor Study Director. This should not affect the administration of the study drug or the continuation of participants in the study.

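### Protocol Section 9 sets no recall deadline, repeat test or dosing rule for isolated, asymptomatic ALT/AST of 3 to <5x ULN, or of 5 to <8x ULN for up to 2 weeks, although 2 to <3x ULN must return within 48-72 hours

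*Protocol*

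**What the plan says.** Protocol Section 9 contains two recall rules.

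- **Upper list.** Treatment-emergent ALT or AST elevations "that reach the thresholds listed below must be managed carefully". There are four entries: at least 8x ULN; at least 5x ULN for more than 2 weeks; at least 3x ULN with total bilirubin above 2x ULN or INR above 1.5; and at least 3x ULN with liver-related symptoms, a term that here includes eosinophilia above 5%. The steps are: "Participants must return to the study site for reevaluation within 48 to 72 hours after the abnormal laboratory results become available for confirmatory testing" of ALT, AST, total and direct bilirubin and INR, with a PK sample. Then: "If prompt evaluation is not possible within 48 to 72 hours after receipt of the abnormal laboratory results, study drug should be interrupted immediately". Also: "The Sponsor Study Director should be notified of laboratory abnormalities and any clinical symptoms within 48 hours of the availability of laboratory results".
- **Lower list.** Treatment-emergent ALT or AST of at least 2x but below 3x ULN. It has its own 48-72 hour return, repeat tests and PK sample. If the elevation is confirmed, with no symptoms and no rise in bilirubin or INR, participants "may continue dosing of study drug and be monitored closely with frequent (eg, at least once weekly) hepatic laboratory testing".

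The permanent discontinuation criteria use the same enzyme levels and qualifiers as the upper list. They add that no other cause is suspected or confirmed and that the elevation persists after study drug is interrupted. A later paragraph requires more frequent testing for confirmed elevations "warranting temporary interruption of study drug but not meeting permanent drug discontinuation criteria as stated above", but does not say which values warrant interruption.

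**The concern.** The two lists do not meet. The lower list stops below 3x ULN. The upper list takes values from 3x ULN only with a qualifier, from 5x ULN only after more than 2 weeks, and without condition only from 8x ULN. Followed as written, a new isolated ALT of 2.5x ULN has a return deadline and a new isolated ALT of 4x ULN has none.

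Two things are at stake. First, the intensity of follow-up should not fall as the enzyme level rises. Second, the entry for at least 5x ULN lasting more than 2 weeks can be recognised only from serial tests, and Section 9 does not order one when such a value is first found. Section 6.6.1 also refers nintedanib users with enzyme elevations to this section, because PLN-74809 is a moderate P-gp inhibitor and may raise nintedanib exposure.

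**Working it through.** **Inputs.** Upper limits from Protocol Table 2: ALT 55 U/L, AST 40 U/L, total bilirubin 1.0 mg/dL. Scheduled chemistry after Day 1, from Appendix 1: Day 14 (±2), Day 28 (±2), Day 56 (±3), Day 84 (±3), Day 98 (±3).

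**Step 1. Run one participant through the rules.** Take a treatment-emergent elevation with no symptoms, bilirubin at most 2x ULN (2 × 1.0 = 2.0 mg/dL) and INR at most 1.5.

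| ALT or AST | ALT, U/L | AST, U/L | Rule that applies |
|---|---|---|---|
| 2 to <3x ULN | 110 to <165 | 80 to <120 | lower list, return in 48-72 h |
| 3 to <5x ULN, any duration | 165 to <275 | 120 to <200 | none |
| 5 to <8x ULN, up to 2 weeks | 275 to <440 | 200 to <320 | none |
| 5 to <8x ULN, over 2 weeks | 275 to <440 | 200 to <320 | upper list |
| ≥8x ULN | ≥440 | ≥320 | upper list |

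The limits are multiples of 55 (2x = 110, 3x = 165, 5x = 275, 8x = 440) and of 40 (80, 120, 200, 320).

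**Step 2. Could the upper-list return paragraph be general?** It directly follows the four listed entries, and the 2 to <3x ULN band is given its own return rule. That second rule would be redundant if the first covered every elevation.

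**Step 3. Does other text fill the gap?**

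- Section 6.2: the Investigator and Sponsor Study Director decide "whether the study drug interruption should be temporary or permanent on a case by case basis". No enzyme threshold is given.
- Section 7.7.1: the Investigator reviews results as they arrive, and clinically significant new abnormalities get further tests if necessary. No deadline.
- Section 7.9 and Appendix 1 footnote f: a PK sample for a liver test abnormality. Section 7.9 places it at a repeat test, so it presupposes one without ordering or timing it.
- Section 9, interruption paragraph: no values given.
- Section 11: discontinuation is allowed for a clinically significant laboratory change, not required.

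None sets a recall time, threshold or dosing rule for these bands. Section 10 shows the contrast. Its Grade 2 and Grade 3 QTc bands adjoin, the recall time shortens from 48-72 hours to 24 hours with severity, and its interruption paragraph lists the qualifying values.

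**Step 4. Timing, assuming that only scheduled chemistry follows a first value of 5 to <8x ULN that persists.** Delay = day of the first scheduled test more than 14 days after the finding − (day of finding + 14).

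- Found at Week 4, seen again at Week 8: 56 − 28 − 14 = 14 days. Range 53 − 30 − 14 = 9 to 59 − 26 − 14 = 19.
- Found at Week 8, seen again at Week 12: 84 − 56 − 14 = 14 days. Range 81 − 59 − 14 = 8 to 87 − 53 − 14 = 20.
- Found at Week 2, Week 4 retest at 14 days or less: that retest cannot show more than 2 weeks, so the next test is Week 8. 56 − 14 − 14 = 28 days. Range 53 − 16 − 14 = 23 to 59 − 12 − 14 = 33.
- Found at Week 2, Week 4 retest later than 14 days: the longest interval is 30 − 12 = 18 days, so the delay is at most 18 − 14 = 4 days.
- Found at Week 12: treatment is ending, so the calculation has little bearing.

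**The case against.** The strongest reply is that the gap matters little in practice. Results are reviewed as they become available, clinically significant abnormalities are to be followed, a PK sample is called for, and interruption can be agreed case by case. An attentive investigator would probably recall a participant at 4x or 6x ULN. The group is also narrow: bilirubin, INR and the differential count are drawn at the same visits, and any qualifier or listed symptom, including fatigue and nausea, brings a value of at least 3x ULN under the upper list. Section 1.1.2 reports no laboratory safety signal. For background therapy, Section 6.2 says "Dose modifications or interruptions of pirfenidone or nintedanib treatment may be implemented only for safety and tolerability reasons", with liver enzyme elevation as its example, and exclusion criterion 18 removes standard-of-care users with relevant earlier elevations. All of this stands and limits the size of the point. It does not supply a deadline or a threshold. The reassurance on dose is also partial: Section 3.2 cites 160 mg for 7 days in healthy participants, and 12 weeks in IPF only at 40 mg.

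Three stronger readings are tempting, and the documents do not support them.

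- A reader might infer that nothing at all happens in these bands. Footnote f calls for a PK sample and Section 7.9 presupposes a repeat test, so what is missing is the order, the deadline and the dosing rule.
- A reader might infer that permanent discontinuation would come 14 or 28 days late. The delay concerns only the duration element. Discontinuation also needs the absence of another cause and enzymes that stay raised after interruption, and the calculation assumes that nobody acts on the result.
- A reader might infer that lighter oversight at 3 to <8x ULN was intended. Express permission to continue dosing appears only at 2 to <3x ULN. That suggests an oversight, but intent is not documented either way.

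**Conclusion.** The point holds and should be fixed. It applies to treatment-emergent elevations only; an unchanged 2.5x ULN carried in from baseline, which the entry criteria allow, would not trigger recall either.

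The timing figures rest on the stated assumption that only scheduled chemistry follows, and on the elevation persisting. They show what the written rules permit and do not forecast what the site would do. The chance that any participant enters these bands cannot be estimated from the documents; about 12 are planned, 8 on active drug. No endpoint or analysis is affected. This is a participant-safety rule that is out of order by severity and can be corrected with wording the protocol already contains.

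**What to change.** Amend Section 9 in two places.

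1. Apply the existing upper-list steps to every treatment-emergent ALT or AST of at least 3x ULN, isolated or not: return within 48-72 hours; repeat ALT, AST, total and direct bilirubin and INR; PK sample; interruption of study drug if prompt evaluation is not possible; notice to the Sponsor Study Director within 48 hours.
2. For confirmed, isolated 3 to <8x ULN that meets no stopping criterion, require at least the close, roughly weekly, hepatic monitoring already given at 2 to <3x ULN, with the decision to continue or interrupt made with the Sponsor Study Director.

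The first change closes the recall gap. The second supplies the serial tests that the 2-week duration entry needs. The stopping criteria can stay as they are. The cost is a wording amendment plus a few unscheduled visits and blood draws at a single center.

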Study drug must be permanently discontinued in the event of QTc prolongation meeting the following criteria:

- Confirmed Grade 3 abnormality: QTcF interval > 500 msec or increased > 60 msec from baseline value
- Grade 4 abnormality (does not require confirmation): torsade de pointes; polymorphic ventricular tachycardia; signs/symptoms of serious arrhythmia

All treatment-emergent QTc abnormalities meeting the criteria for permanent discontinuation (as listed above) must be reported to the Sponsor Study Director within 48 hours. The participant must permanently discontinue study drug immediately and continue to be followed for close monitoring and causality and clinical evaluation as follows:

- Repeat ECG at least once weekly until abnormalities stabilize (ie, QTc interval is comparable to baseline value or baseline grade of abnormality, if applicable) and the participant is asymptomatic
- Correction of any electrolyte abnormalities, if applicable
- Obtain a detailed history of symptoms and comorbidities
- Obtain a history of concomitant drug use (including nonprescription or over-the-counter medications and herbal and dietary supplement preparations)
- Consider a cardiology consultation

For participants with confirmed QTc prolongation (as described below) warranting temporary interruption of study drug but not meeting permanent drug discontinuation criteria, more frequent ECG testing and clinical assessments (at least once weekly) must be performed using unscheduled visits, including a thorough causality evaluation and in consultation with the Sponsor Study Director.

- Confirmed Grade 2 QTcF interval > 480 but ≤ 500 msec
- Confirmed increased > 30 to ≤ 60 msec from baseline value

Re-initiation of study drug can only be considered if a more likely etiology is identified and if ECG abnormalities have returned to baseline values. **The decision to restart study drug must be discussed and approved in consultation with the Sponsor Study Director prior to re-initiation.** More frequent clinical monitoring and ECG assessments (at least once weekly) after re-initiation of study drug, if applicable, should be performed through use of

unscheduled visits. **If the QTc prolongation reoccurs upon re-challenge, study drug must be permanently discontinued.**

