Any participant who experiences a QTc prolongation not confirmed upon repeat ECG assessment may continue or resume administration of study drug and follow the scheduled study visits, if clinically appropriate. More frequent clinical evaluation and ECG monitoring through use of unscheduled visits is allowed, if clinically warranted.

Participants who permanently discontinue study drug due to potential QTc prolongation must be followed for close monitoring until abnormalities stabilize to baseline levels or baseline grade of abnormality and the participant is asymptomatic. Participants should be encouraged to remain in the study and completed all scheduled visits and assessments. Long-term follow-up information should be provided for participants who permanently discontinue drug due to confirmed QTc prolongation, including information on corrective therapy and cardiology consultation, if applicable.

11 **EARLY DISCONTINUATION OF STUDY OR INDIVIDUAL PARTICIPANTS**

In accordance with the Declaration of Helsinki, participants have the right to withdraw from the study at any time for any reason. The Investigator or Sponsor may withdraw a participant from the study or discontinue study drug for any of the following reasons:

- Noncompliance with protocol procedures including those relating to administration of study drug
- A serious or intolerable AE occurs
- Infection with COVID-19 that precludes safe participation in the study
- A clinically significant change in a laboratory parameter occurs
- Confirmed elevations in serum ALT or AST meeting criteria for suspected acute DILI (see [Section 9](#))
- Prolonged ECG QTc interval meeting criteria for permanent discontinuation (see [Section 10](#))
- Male participants whose female partners become pregnant during the study must stop the medication immediately
- The Sponsor or Investigator terminates the study
- The participant requests to be discontinued from the study

If a participant is withdrawn from the study or discontinues study drug, they will undergo early termination assessments; refer to the Schedule of Events ([Appendix 1](#)).

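### Protocol Section 9 makes every mandatory liver stop depend on a study drug interruption that it does not order when the confirmatory retest is done on time

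*Protocol*

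**What the plan says.** Protocol Section 9 sets four upper thresholds for treatment-emergent ALT or AST, as multiples of the upper limit of normal (ULN):

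- 8 times or more
- 5 times or more for over 2 weeks
- 3 times or more with total bilirubin above 2 times ULN or INR above 1.5
- 3 times or more with liver-related symptoms

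A participant who reaches one must be retested within 48 to 72 hours of the result. Section 9 then gives its only order to hold the drug: "If prompt evaluation is not possible within 48 to 72 hours after receipt of the abnormal laboratory results, study drug should be interrupted immediately".

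Three criteria for permanent discontinuation follow. Each needs a confirmed elevation and each ends with the same proviso: "if no other etiology is suspected/confirmed and liver enzymes are sustained following interruption of study drug". When they are met, the participant must stop for good at once, and the Sponsor Study Director must be told within 48 hours.

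Three other parts of Section 9 bear on the point:

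- Participants confirmed at 2 to below 3 times ULN, without symptoms or raised bilirubin or INR, "may continue dosing of study drug and be monitored closely with frequent (eg, at least once weekly) hepatic laboratory testing".
- A later paragraph begins "For participants with confirmed elevations in liver enzymes (as described above) warranting temporary interruption of study drug". It requires closer testing of these participants if they fall short of the permanent-stop criteria.
- The restart rule reads: "Reinitiation of study drug can only be considered if another etiology is identified and confirmed and if liver abnormalities have returned to baseline values".

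Outside Section 9, Section 6.2 leaves interruption to case-by-case judgement. Section 11 lists reasons for which the drug may be stopped, including "A clinically significant change in a laboratory parameter occurs".

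**The concern.** A participant retested late is told to stop dosing while waiting. A participant retested on time, with a confirmed and possibly serious elevation, is given no such instruction. The permanent-stop criteria then ask whether the enzymes stayed raised after an interruption that nobody was told to start.

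Section 9 also conflicts with itself. It requires an immediate permanent stop once the criteria are met, yet the criteria need a prior hold and a later test.

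Two other rules rest on the same criteria: the 48-hour report to the Study Director, and the Section 8.8.1 example of an important medical event (laboratory values that meet the suspected drug-induced liver injury criteria and lead to permanent discontinuation). An unclear criterion therefore affects safety classification as well as dosing. The protocol itself flags liver monitoring: Section 6.6.1 asks for it in nintedanib users because PLN-74809 is a moderate P-gp inhibitor.

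**Working it through.** The plan gives no figure to reproduce. The check traces the decision rules.

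**1. The thresholds in units.** Table 2 gives upper limits of 55 U/L for ALT, 40 U/L for AST and 1.0 mg/dL for total bilirubin.

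- 8 times: ALT 8 × 55 = 440; AST 8 × 40 = 320 U/L
- 5 times, for over 2 weeks: ALT 5 × 55 = 275; AST 5 × 40 = 200 U/L
- 3 times: ALT 3 × 55 = 165; AST 3 × 40 = 120 U/L, with bilirubin above 2 × 1.0 = 2.0 mg/dL, INR above 1.5, or symptoms

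**2. The two paths from an upper-threshold result.**

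| | Retest not possible in 48 to 72 h | Retest on time, elevation confirmed |
|---|---|---|
| Hold ordered in Section 9? | Yes | No |
| Can persistence after interruption be tested? | Yes | Only if someone chooses to interrupt |
| Can the mandatory stop be reached by following the text? | Yes | Not without that choice |

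The persistence proviso is in 3 of 3 permanent-stop criteria. On the on-time path, 0 of 4 upper thresholds carries an ordered hold.

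**3. Search for another order to interrupt.**

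- *Section 9, permission to continue.* It is given only at 2 to below 3 times ULN. This implies that dosing should not simply go on above that level, but it does not order a hold.
- *Section 9, paragraph on temporary interruption.* It presupposes that some confirmed elevations are held and points back to earlier text. That text contains no instruction to hold on confirmation. What the paragraph requires is more testing.
- *Section 9, notice to the Study Director.* This is notification only.
- *Section 6.2.* It applies if the drug needs to be interrupted and sets no liver trigger.
- *Section 11.* It is permissive.
- *SAP 5.12.3.* It summarises laboratory results and sets no dosing rule.

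None of these orders a hold for the on-time, confirmed case.

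**4. Comparison with the QTc rules.** Section 10 also retests first and also orders interruption when evaluation cannot be prompt. It differs in two ways. A confirmed Grade 3 QTcF value requires a permanent stop with no persistence condition. And the paragraph beginning "For participants with confirmed QTc prolongation (as described below) warranting temporary interruption of study drug" goes on to list the values meant: above 480 to 500 msec, or an increase above 30 to 60 msec. Section 9 has no matching list.

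**The case against.** The strongest reply is to read Section 9 as a whole: retest, interrupt, then decide on permanence. The paragraph on temporary interruption refers to elevations already described. Since the 2 to below 3 times band may continue dosing, elimination points mainly to the upper thresholds. On this view a hold is plainly intended and only the imperative is missing. The practical safeguards are also real. The Study Director should hear within 48 hours of the result, Sections 6.2 and 11 allow the drug to be stopped, and a hold once begun is hard to reverse. This is a single-center study of about 12 participants, and a competent investigator would probably interrupt.

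Most of that stands. It lowers the chance of harm and shows that a pathway exists. It does not supply the missing instruction, and the stop rule cannot work without it.

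A reader might infer three stronger things that the documents do not support:

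- *That Section 9 allows dosing to continue at high values.* It does not. Its express permission stops below 3 times ULN.
- *That dosing could run unchecked to the next scheduled chemistry sample, so that a number of extra doses can be counted.* Appendix 1 schedules chemistry at screening, Day 1 and Weeks 2, 4, 8, 12 and 14. Nominal gaps reach 28 days, and the visit windows can alter them. But Section 7.7.1 calls for clinically significant new abnormalities to be followed with additional tests as needed until explained or resolved. A threshold that must last more than 2 weeks itself implies serial samples. No dose count follows from the text.
- *That retesting before holding is itself the fault.* Section 10 uses the same order, and it is a defensible choice.

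**Conclusion.** The point holds and is worth correcting. For a participant retested on time and confirmed at any of the four upper thresholds, none of the three mandatory stop criteria can be assessed until someone makes a discretionary decision to interrupt. The gap is confined to starting the hold, because the restart rule is strict once a hold exists. Its likely effect on exposure cannot be quantified from the documents and is probably small.

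This rests on reading Section 9 as written and on no separate study manual ordering the hold; Section 9 refers to none. The point concerns participant safety and the classification of liver cases. It does not affect the primary analysis.

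**What to change.** Add one sentence to Section 9 after the retest instructions:

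> *If the retest confirms an elevation at any of the thresholds listed above, study drug must be interrupted immediately; the interruption continues while the permanent-discontinuation criteria are assessed, with hepatic tests at least weekly, and the restart rule in this section applies.*

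The existing sentence on late retests stays. The cost is a protocol amendment, some unscheduled hepatic tests for the few participants affected, and some missed doses in a confirmed case later given another cause. Scheduled visits and sample size do not change.

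Two further changes are clinical choices for the sponsor and are not needed to close the gap:

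- *Hold from the first, unconfirmed result.* For an elevation that is not confirmed, this would cost about 2 to 3 of 84 daily doses (2/84 = 2.4%; 3/84 = 3.6%), plus laboratory turnaround. The PK sample at the retest would fall 2 to 3 days after the last dose. The restart rule would need an exception, which could follow Section 10, where participants with unconfirmed QTc prolongation "may continue or resume administration of study drug and follow the scheduled study visits, if clinically appropriate".
- *Drop the persistence proviso.* With the proviso kept, a participant whose enzymes fall off drug does not meet the suspected liver injury criteria, even if no other cause is found. The restart rule would still keep that participant off drug, so the choice mainly affects how the case is classified and reported.
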